HRPP	Human Research Protections Program
ICI	Immune Checkpoint Inhibitor
IDE	Investigational Device Exemption
IHC	Immunohistochemistry
IND	Investigational New Drug
IV (or iv)	Intravenously
MIBC	muscle invasive bladder cancer
MRI	Magnetic Resonance Imaging
MTD	Maximum Tolerated Dose
NACT	Neoadjuvant chemotherapy
NCI	National Cancer Institute
ORR	Overall Response Rate
OS	Overall Survival
PBMCs	Peripheral Blood Mononuclear Cells
pCR	Pathologic Complete Response
PD	Progressive Disease
PET	Positron Emission Tomography
PFS	Progression Free Survival
p.o.	per os/by mouth/orally
PR	Partial Response
PULSAR	Personalized ULtrafractionated Stereotactic Adaptive Radiotherapy

RCB	Residual Cancer Burden
RECIST	Response Evaluation Criteria in Solid Tumors
RFS	Recurrence Free Survival
SAbR	Stereotactic Ablative Radiotherapy
SAE	Serious Adverse Event
SCCC	Simmons Comprehensive Cancer Center
SD	Stable Disease
SGOT	Serum Glutamic Oxaloacetic Transaminase
SoC	Standard of Care
SPGT	Serum Glutamic Pyruvic Transaminase
WBC	White Blood Cells

STUDY SCHEMA

STUDY SUMMARY

Title	Checkpoint Inhibitor and Radiation Therapy in Bulky Node-Positive Bladder Cancer (CIRTiN-BC): A Phase II, Single-Arm Trial
Short Title	CIRTiN-BC
Protocol Number	STU-2021-0114
Phase	Phase I/II
Methodology	Single-arm safety/efficacy trial
Study Duration	36 months
Study Center(s)	Single center at UT Southwestern Medical Center, with potential expansion to Parkland Hospital and John Peter Smith Hospital
Objectives	To evaluate the safety and efficacy of PULSAR in patients with bulky node-positive bladder cancer on immune checkpoint inhibitor therapy due to ineligibility for or failure to respond to downstaging chemotherapy
Number of Subjects	27
Diagnosis and Main Inclusion Criteria	bladder cancer with bulky regional lymph node metastases, planning immune checkpoint inhibitor therapy due to ineligibility for downstaging chemotherapy or failure to respond to downstaging chemotherapy
Study Product(s), Dose, Route, Regimen	PULSAR (personalized ultrafractionated stereotactic ablative radiotherapy) 30 Gy in 3 fractions
Duration of administration	3 fractions at 12 - 16 day intervals
Reference therapy	standard of care with systemic therapy alone, followed by radical cystectomy if treatment response

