1.0 BACKGROUND AND RATIONALE

1.1 Disease Background

Muscle invasive bladder cancer (MIBC) has high metastatic potential and warrants aggressive treatment. Standard-of-care treatment in MIBC involves platinum-based neoadjuvant chemotherapy (NACT) followed by radical cystectomy (RC) with pelvic lymph node dissection (PLND) and urinary diversion¹⁻³. Bladder-conserving chemoradiation therapy is an appropriate alternative in select patients, though it is used in only a minority of cases in the United States⁴. Bladder cancer carries significant morbidity and mortality and has been cited as the most expensive malignancy to manage, on a per-patient basis, in the United States^{5,6}.

Metastatic spread to regional lymph nodes is an adverse prognostic factor in bladder cancer. In several large case series reported without use of neoadjuvant chemotherapy, patients with pathologically positive lymph nodes (pN+) at radical cystectomy had 5-year overall or disease-specific survival rates of only 22-30%⁷⁻¹⁰. The addition of neoadjuvant chemotherapy (NACT) or downstaging chemotherapy (DCT) in patients with clinically positive lymph nodes (cN+) improves outcomes, particularly in those who achieve a pathologic complete response to DCT^{11,12}. However, patients who fail to respond to downstaging or neoadjuvant chemotherapy have an especially poor prognosis, with a 5-year overall survival rate of only 16% in one recent series¹³. It should also be noted that a significant proportion (up to 25-50%) of patients with bladder cancer are ineligible for chemotherapy due to medical comorbidities¹⁴.

We recently reviewed the outcomes of patients undergoing radical cystectomy at UT Southwestern with bulky cN+ bladder cancer¹⁵. Among the subset of patients who did not receive or failed to respond to DCT, the 2-year progression-free survival was only 30%, despite aggressive salvage treatment. Importantly, a majority of patients (84%) in the study received downstaging chemotherapy and all were medically eligible for chemotherapy. This suggests that chemo-ineligible patients presenting with cN+ disease were not offered curative treatment. Direct comparisons with historic literature are difficult, due to widely varying definitions of cN+ disease; however, the progression-free survival of our bulky cN+ cohort closely parallels that of the cN2-3 and cM1a cohorts within one large published series¹¹, confirming that our bulky cN+ cohort represents an especially high-risk population.

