1.3 Immune Checkpoint Inhibitor Therapy

Immune checkpoint inhibitor (ICI) therapy has assumed increasing importance in the management of bladder cancer. ICI agents function to nonspecifically stimulate the patient's immune response and decrease tumor immune evasion by inhibiting negative regulators of the immune response. In bladder cancer, most interest has attached to monoclonal antibodies which block the immunosuppressive surface receptor PD-1 or its ligand PD-L1²⁵.

Three PD-1 or PD-L1 inhibitors (avelumab, nivolumab, and pembrolizumab) are FDA-approved for second-line use in platinum-refractory advanced bladder cancer, based on clinical trials which showed objective response rates of 15-20%²⁶⁻³⁰. Two agents (atezolizumab and pembrolizumab) are FDA-approved for first-line use in patients who are ineligible for platinum-based chemotherapy, based on clinical trials showing objective response rates of 25-30% in this setting^{31,32}. Finally, avelumab has recently gained FDA approval for use as maintenance therapy following initial response to chemotherapy in advanced/metastatic bladder cancer, with clinical trials demonstrating an improvement in median overall survival from 14 to 21 months³³.

More recent efforts have explored a role for ICI treatments in the neoadjuvant setting. Two clinical trials, ABACUS and PURE-01, explored the use of neoadjuvant atezolizumab and pembrolizumab respectively, and reported pathologic complete response (pCR, meaning ypT0 N0) rates of 31% and 37%, respectively^{34,35}. While several other ongoing trials exist in this space, only a single trial has enrolled significant numbers of patients with clinical node-positive disease. In this trial, NABUCCO, patients with cN+ disease represented 42% of total enrollment. Neoadjuvant treatment with dual ICI agents (the PD-1 inhibitor nivolumab and the CTLA-4 blocker ipilimumab) resulted in an overall pCR rate of 46%³⁶.

Given their widespread clinical use in bladder and other malignancies, the adverse effect profile of ICI agents is well characterized. In the second-line trials cited above, for example, grade ≥ 3 adverse events occurred in 5-18% of patients and most notably

included autoimmune reactions at various sites including pneumonitis, colitis, and hepatitis²⁶⁻³⁰.

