9.2 Sample Size and Accrual

For the primary endpoint of feasibility, we define a target rate of protocol completion (completion of radical cystectomy within sixteen weeks of initiation of PULSAR) of 90%, with a lower boundary of futility at 60%. A sample size of 24 patients provides 91% power to reject a 60% completion rate at a two-sided alpha of 0.05. Of note, this sample size was employed in the recent NABUCCO trial, which addressed a similar high-risk patient cohort³⁶. Allowing a 10% drop out rate increases the desired enrollment to a total of **27 patients**. Given the desired enrollment of 27 patients and the three-year trial period, this will require accrual of nine patients per year across all sites.

For the secondary endpoint of progression-free survival, the trial-eligible subset of our recently published historic series of cN+ bladder cancer patients achieved a 2-year recurrence-free survival rate of 30%¹⁵. A sample size of 24 patients provides 90% power to detect a 27% absolute increase in 2-year recurrence free survival with a one-sided alpha of 0.10 using the Kaplan-Meier log-rank test.

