9.3 Data Analyses

The primary endpoint, protocol completion, will be assessed by calculating the proportion of patients completing radical cystectomy within sixteen weeks of initiating PULSAR treatment. If the proportion of patients undergoing cystectomy exceeds 60%, the null hypothesis (that use of ICI+PULSAR+RC is not feasible) will be deemed to have been rejected.

For the secondary endpoint, progression-free survival will be determined as described above, and will be reported by means of Kaplan-Meier survival curves, median progression-free survival time, and proportion of patients without progression at two years. Comparison will be made to the trial-eligible subset of patients in a historic control series using the log-rank test. The 2-year progression-free survival rate in the historic cohort was 30%. The null hypothesis will be rejected if the one-sided *p* value for the comparison is less than 0.10.

Additional planned analyses include the following, all of which will be reported with simple descriptive statistics (*n* / *N* and percentage):

Major complication rate: A major surgical complication will be defined as any postoperative complication of Clavien-Dindo Grade III or higher.

Pathologic outcomes: Pathologic outcomes will be defined as follows, based on the final surgical pathology report:

1. Pathologic complete response: no viable disease remaining in the specimen (ypT0 N0).
2. Pathologic non-muscle-invasive downstaging: primary tumor without muscle invasion, and no viable disease in lymph nodes (\leq ypT1 N0).
3. Pathologic organ-confined downstaging: primary tumor confined to detrusor muscle, and no viable disease in lymph nodes (\leq ypT2 N0).
4. Nodal complete response: no viable disease in lymph nodes, regardless of primary tumor stage (ypTany N0).

Residual disease: Residual disease at surgery will be defined as follows:

1. Microscopic residual disease (R1) will be defined as any positive soft tissue margin on the final surgical pathology report, excluding carcinoma *in situ* at ureteral margins.
2. Gross residual disease (R2) will be defined as any grossly positive tissue margin reported on a pathology report, *or* the operating surgeon's subjective report of grossly unresectable disease including bulky matted lymph nodes.

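### The 9.3 progression-free survival test compares the whole ICI + PULSAR + cystectomy regimen with a historic cohort not shown to have had preoperative ICI, so it cannot separate a PULSAR effect from an ICI effect

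*Combined protocol and SAP*

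**What the plan says.** The Study Summary gives the objective as "To evaluate the safety and efficacy of PULSAR in patients with bulky node-positive bladder cancer on immune checkpoint inhibitor therapy". PULSAR is the only study product listed there. The reference therapy is "standard of care with systemic therapy alone, followed by radical cystectomy if treatment response".

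ICI is background treatment. Section 4.1 has it started before PULSAR and continued through it, and section 4.8 treats it as standard of care.

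Section 9.1 calls the secondary endpoint efficacy. Section 9.3 tests it formally: "Comparison will be made to the trial-eligible subset of patients in a historic control series using the log-rank test". It adds "The 2-year progression-free survival rate in the historic cohort was 30" per cent, and rejects when the one-sided p "value for the comparison is less than 0.10".

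Section 1.1 describes the source of the benchmark, an institutional series of cystectomy patients: "Among the subset of patients who did not receive or failed to respond to DCT, the 2-year progression-free survival was only 30" per cent, in spite of salvage treatment whose type is not given. Neither section reports ICI use or the number of patients in the subset.

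Section 9.2 gives the design figure: "A sample size of 24 patients provides 90% power to detect a 27% absolute increase in 2-year recurrence free survival", at a one-sided alpha of 0.10.

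**The concern.** The question posed is what PULSAR adds in patients already on ICI. The comparison that answers it sets ICI + PULSAR + cystectomy against cystectomy patients selected by chemotherapy status. If those patients had little or no preoperative ICI, two things differ between the groups, and the test sees only their sum.

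The protocol itself gives grounds for thinking that ICI alone is active. For first-line ICI in platinum-ineligible patients, section 1.3 cites "clinical trials showing objective response rates of 25-30% in this setting". It also reports 15-20% in platinum-refractory disease, and pathologic complete response of 31% and 37% in two single-agent neoadjuvant trials. None of these is a 2-year PFS in bulky node-positive disease, so they show that an ICI contribution is plausible but not how large it is.

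At stake is what a positive secondary result may be said to show. Nothing in the plan adjusts the benchmark for ICI or limits the claim.

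**Working it through.** **1. Reproduce the plan's figure.** Inputs from 9.2 and 9.3: n = 24, null 2-year PFS 0.30, alternative 0.30 + 0.27 = 0.57, one-sided alpha 0.10. Treat 2-year status as binary and reject when X ≥ r, with P(X ≥ r | p) = Σ C(24,k) p^k (1−p)^(24−k), k = r to 24.

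- r = 10: P at 0.30 = 0.153, above 0.10.
- r = 11: P at 0.30 = 0.074, and P at 0.57 = 0.904.

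The rule is therefore at least 11 of 24, and its power of 90.4% agrees with the stated 90%. The arithmetic of the plan is not at fault.

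**2. Let ICI alone move the rate, with no PULSAR effect.** The documents give no 2-year PFS for ICI plus cystectomy without PULSAR. I assume 35 to 50%, and assume that the cohorts are otherwise alike.

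The same 11-of-24 rule is evaluated at each rate. Because 9.3 names a log-rank test, I also simulated a two-sample log-rank: exponential times with hazard −ln(S)/2 per year, where S is 2-year PFS (0.602 for S = 0.30), follow-up ending at 2 years, 24 trial patients, and rejection when (E − O)/√V > 1.2816 in the trial arm. There were 40,000 replicates per cell (standard error about 0.25 points or less). The number of controls is not in the documents, so 12 to 100 are shown.

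| Assumed 2-year PFS, ICI + cystectomy | 11 of 24 | Log-rank, 24 controls | Log-rank, 12 to 100 controls |
|---|---|---|---|
| 30% (null) | 7% | 10% | 9-11% |
| 35% | 18% | 19% | 18-20% |
| 40% | 35% | 31% | 27-36% |
| 45% | 55% | 44% | 37-54% |
| 50% | 73% | 58% | 49-71% |

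An assumed ICI gain of 10 points (30% to 40%) would thus give a positive test in about a third of trials in which PULSAR does nothing.

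**3. What an ICI-based benchmark would cost.** Keep n = 24, alpha 0.10 and a true rate of 57%, and choose the smallest r with P(X ≥ r | benchmark) ≤ 0.10.

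| Benchmark | r | Power at n = 24 | n for about 90% power |
|---|---|---|---|
| 35% | 12 | 82% | 34 |
| 40% | 14 | 53% | 59 |
| 45% | 15 | 37% | 121 |
| 50% | 16 | 23% | 339 |

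The trial as sized cannot do much against a higher benchmark, so the realistic remedy is a narrower claim.

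**The case against.** The strongest reply is that the plan mostly speaks of the regimen already. Section 9.3 attributes nothing to PULSAR. Section 2.2.1 sets out to determine PFS in all enrolled patients and in those completing ICI + PULSAR + cystectomy, and section 1.4 places its hope in the combined treatment. That stands: the mismatch lies between the Study Summary objective and the test, and a reader who infers that 9.3 itself credits PULSAR goes beyond the text.

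Two more tempting readings also fail.

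- *The Study Summary names ICI as the reference.* It says systemic therapy. Section 1.4 explains downstaging systemic therapy as chemotherapy, ICI or both. For patients who cannot have, refuse or have not responded to platinum, that means ICI in practice, but this is an inference.
- *The historic patients had no ICI.* Their ICI use is unreported. The salvage treatment could have included it, although salvage is not the same as preoperative ICI.

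The bias may also run the other way. By section 1.1 the historic patients all reached cystectomy and were all medically fit for chemotherapy. The trial counts everyone enrolled and admits chemotherapy-ineligible patients, which could lower its PFS and offset an ICI gain. This too stands. It removes any claim about the sign of the bias, but makes a rejection no easier to read as a PULSAR effect.

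Finally, this is a limit shared by single-arm phase II trials and concerns a secondary endpoint. True, but the endpoint has its own power, alpha and rejection rule, so its meaning should be stated.

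**Conclusion.** The point holds as a limit on interpretation. The test concerns the combined regimen against a benchmark not shown to be ICI-treated, so a rejection cannot by itself support the Study Summary objective.

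The rejection rates of 18 to 73% (11-of-24 rule) or about 19 to 58% (log-rank, 24 assumed controls) rest on an assumed ICI-only PFS of 35 to 50%, on no PULSAR effect, and on cohorts that are alike in all else. A reader might take them as the trial's false-positive rate, or conclude that the comparison favours the trial. The documents support neither: they give no ICI-only PFS and no ICI exposure or size for the historic subset, and the two populations differ in ways that could work against the trial.

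The primary feasibility endpoint and its test are not touched.

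**What to change.** 1. In 9.3 and the Study Summary, state that rejecting the 30% benchmark concerns ICI + PULSAR + cystectomy as a regimen and is not evidence for PULSAR over ICI alone.
2. Report 2-year PFS with its one-sided 90% lower confidence bound, so that it can be set against any ICI-only rate that becomes available. For scale, with complete follow-up the exact bound (the 10% quantile of Beta(x, 25 − x) for x of 24 progression-free) is 31% for 11 of 24 and 43% for 14 of 24. A result near the 57% target (14/24 = 58%) would therefore still not exclude an ICI-only rate of 45%.
3. Report the size of the trial-eligible historic subset and how many of its patients had ICI, and whether before surgery or as salvage. Add a comparison restricted to ICI-exposed historic patients only if there are enough of them; there may be none.

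The cost is a few sentences, one confidence bound and a small tabulation from the institution's own series. No added patients and no change of design are needed. The price is a narrower efficacy claim.

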6.1.6 Progression-Free Survival

Progression-free survival (PFS) is defined as the duration of time from start of PULSAR treatment to time of progression. Progression is defined as any of:

1. Radiologic disease progression, as defined by RECIST 1.1 criteria above.
2. Pathologic demonstration of recurrent or metastatic disease (e.g. core needle biopsy, fine needle aspirate, diagnostic peritoneal lavage).
3. Initiation of a patient on salvage or palliative treatment due to clinical concern for disease progression.
4. For patients with documented concern (by the operating surgeon) for grossly incomplete disease resection (R2) including bulky unresectable lymph nodes, the date of the first postoperative imaging study showing disease progression by RECIST 1.1 criteria.

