9.0 STATISTICAL CONSIDERATIONS

9.1 Study Design/Study Endpoints

This is a single institution, single arm, phase II trial. We hypothesize that the combination of standard-of-care ICI with PULSAR will be feasible and does not result in delays in treatment. We define a target rate of protocol completion (completion of radical cystectomy within sixteen weeks of initiation of PULSAR) of 90%, with a lower boundary of futility at 60%.

The secondary endpoint is efficacy, defined by 2-year recurrence-free survival.

As discussed above, we additionally plan to assess safety (defined by the 90-day rate of Clavien-Dindo Grade \geq III complications following radical cystectomy); pathologic outcomes; rates of residual disease at surgery; and ureteroenteric anastomotic stricture rate.

If the incidence of Grade 3 or higher treatment-related adverse events convincingly exceeds 50%, a threshold we are comfortable with given the potential benefit of the regimen as well as our experience in managing the side effects in this patient population, we will temporarily halt the study and carefully review the available data at that point in order to suggest a potential modification. If we determine that high rates of adverse events are intrinsically related to protocol and no modification will reasonably decrease this rate to an acceptable threshold (below 50%), then we will terminate the study.

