Ureteroenteric stricture rate, defined as the need for procedural intervention performed for decompression of an obstructed kidney (e.g. percutaneous nephrostomy tube or surgical revision of ureteroenteric anastomosis), unless due to known or suspected disease recurrence.

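### The stricture rule in section 9.3 excludes only disease recurrence, so postoperative decompression for a stone, and on a literal reading for residual R2 disease, counts as a ureteroenteric stricture

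*Combined protocol and SAP*

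**What the plan says.** Section 9.1 lists, among the outcomes to be assessed beyond the primary and secondary endpoints, "rates of residual disease at surgery; and ureteroenteric anastomotic stricture rate". Section 9.3 defines the stricture outcome as "the need for procedural intervention performed for decompression of an obstructed kidney". Its two examples are a nephrostomy and a revision of the anastomosis, and it makes one exception: "unless due to known or suspected disease recurrence". That is the whole rule. It does not ask what caused the obstruction, apart from recurrence, or where it lies. Section 9.3 reports these additional outcomes as n/N and a percentage, but does not say who makes up N for stricture.

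Residual disease is handled elsewhere as a separate matter. In 9.3, R2 is an outcome of its own and includes "the operating surgeon's subjective report of grossly unresectable disease including bulky matted lymph nodes". In section 6.1.6, item 4, a patient with R2 disease is dated as progressed at "the date of the first postoperative imaging study showing disease progression by RECIST 1.1 criteria". Under that item, R2 disease is not progression until imaging shows growth or new lesions.

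The protocol is not strict with the word recurrence. Section 9.1 calls the secondary endpoint recurrence-free survival, 9.3 calls it progression-free survival, and 9.2 uses both terms for one endpoint.

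**The concern.** The name of the outcome and the rule that scores it do not match. The name refers to a narrowing at the anastomosis. The rule counts a procedure, and one of its two examples (nephrostomy) is not specific to any cause or site of obstruction. With a single exclusion, other reasons for the same procedure fall into the count.

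This population makes the R2 case foreseeable. Eligibility requires bulky pelvic nodes, section 1.4 does not withhold cystectomy solely because those nodes enlarge, and the plan writes rules for R2 resection. The dose-constraint table in 4.6 names stenosis as the radiation endpoint for the ureter, so readers are likely to look at the stricture rate as a possible harm of PULSAR before surgery. A rate that mixes anastomotic stricture with stones and tumour compression would answer that question poorly.

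**Working it through.** The documents state no stricture rate, threshold or sample size, so there is no figure to reproduce. The check has two parts.

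**1. Apply the rule as written.** Take a patient who has had cystectomy, has a ureteroenteric anastomosis, and later has an obstructed kidney decompressed.

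| Cause of obstruction | Caught by the exclusion? | Scored as stricture? |
|---|---|---|
| Narrowing at the anastomosis | No | Yes, correctly |
| Known or suspected recurrent tumour | Yes | No, correctly |
| Stone | No | Yes, incorrectly |
| R2 nodes left at surgery, stable on imaging | Not literally: residual disease is neither recurrent nor, under 6.1.6 item 4, progressed | Yes on the literal reading; an assessor might exclude it |
| R2 nodes that have progressed on imaging | Only if recurrence is read to include progression | Depends on the assessor |

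The stone row follows from the plain wording. The two R2 rows depend on how broadly recurrence is read.

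**2. Size of one misclassified patient.** If k patients are wrongly counted among N, the reported rate rises by 100 × k/N points. Section 9.3 gives no N, so a range is needed. Section 9.2 gives 24 (the size used for the completion-rate calculation) and 27 (enrolment). Neither is a count of patients with an anastomosis. At the target completion rate, 0.90 × 27 = 24.3 patients; at the futility boundary, 0.60 × 27 = 16.2. I take N = 16, 24 and 27 as assumptions.

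| k | N = 16 | N = 24 | N = 27 |
|---|---|---|---|
| 1 | 1/16 = 6.25 points | 1/24 = 4.2 points | 1/27 = 3.7 points |
| 2 | 2/16 = 12.5 points | 2/24 = 8.3 points | 2/27 = 7.4 points |

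For scale, exact (Clopper-Pearson) 95% intervals at N = 24 are 0 to 14.2% for no events, 0.1 to 21.1% for one and 1.0 to 27.0% for two. One wrongly counted patient is therefore visible in the point estimate but well inside the sampling uncertainty. The documents do not say how often such decompressions occur, so k is unknown.

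**The case against.** An intervention-based definition is a legitimate and objective proxy, and the plan has already thought about malignant obstruction. The exclusion covers suspected as well as known recurrence, and the protocol treats recurrence and progression almost as synonyms. A sensible assessor would probably exclude a ureter compressed by tumour. This stands in part: for R2 disease the defect is an ambiguity, not a certain miscount. But the word suspected relaxes the certainty needed, not the category, and R2 disease has its own definition a few lines above. Two assessors could score the same patient differently. The objection does not reach stones.

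A reader might also infer that the rule sweeps in patients who never had cystectomy, or who had a nephrostomy before it. The documents do not support that. Both 9.1 and 9.3 name a ureteroenteric outcome, which presupposes an anastomosis. The missing denominator is worth stating, but it does not turn those patients into strictures.

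Finally, the outcome has little formal weight. It is descriptive, with no comparator or test. The main surgical safety measure in 9.1 is the 90-day rate of Clavien-Dindo Grade III or higher complications, and the stopping rule uses Grade 3 or higher adverse events. This stands in full and limits the importance of the point.

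**Conclusion.** The point holds in a limited form. As written, 9.3 counts postoperative decompression for a stone as a ureteroenteric stricture and, read literally, does the same for obstruction by residual R2 disease. Each such patient moves the reported rate by about 4 points if N is near 24, and by about 6 if only 16 patients have an anastomosis (an assumption).

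A reader might infer that the reported rate will be a stated multiple of the true rate, or that the trial will produce a false harm signal. Neither can be shown. Any multiple would need both a true stricture rate and a rate of other decompressions, and the documents give neither. No decision depends on this rate, and the primary endpoint, PFS and the stopping rule are unaffected. This is a worthwhile clarification, not a flaw in the design.

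**What to change.** Reword the stricture definition in 9.3 as follows:

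- Count procedural decompressions of an obstructed kidney after cystectomy, among patients with a ureteroenteric anastomosis, and state that group as N.
- Extend the exclusion to *known or suspected recurrent, residual (R2) or progressive disease, or another identified non-anastomotic cause such as stones*.
- List the excluded decompressions separately with their cause, so that no event is hidden.

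Do not make documented localisation at the anastomosis a condition. That could lose true strictures whose site was never recorded. An obstruction with no other identified cause should remain counted.

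The cost is a few lines of text, a little extra chart abstraction, and some judgement of cause. The change is best made before any of these events are classified.
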